- **3. Otras infecciones de transmisión sexual (ITS):** Se recomienda el cribado universal de sífilis a todos los inmigrantes procedentes de un país incluido en la definición de población diana si no se ha hecho una prueba de sífilis con anterioridad. Repetir prueba de sífilis si la persona es diagnosticada con otra ITS y/o presenta otros factores de riesgo.
- **4. Virus de la hepatitis B (VHB)**: Se recomienda realizar el cribado de VHB mediante la detección del antígeno australiano (HBsAg) y el anticuerpo contra el antígeno core (anti-HBc) a todos los inmigrantes procedentes de un área con prevalencia intermedia o alta de VHB (≥2%). *Además, se ofrecerá cribado de VHB a inmigrantes procedentes de Marruecos y Guinea Ecuatorial, aunque la prevalencia en estos países es <2%.

Se ofrecerá pauta vacunal a las personas con un test serológico negativo.

- **5. Virus de la hepatitis C (VHC):** En el contexto del plan para la eliminación de la hepatitis C en Andalucía, se recomienda el cribado universal de VHC a todos los inmigrantes procedentes de un país incluido en la definición de población diana.
- **6. Tuberculosis (TB) activa:** Se recomienda el cribado de TB por Mantoux a inmigrantes asintomáticos recién llegados (<5 años) procedentes de países con una incidencia >50 casos/100.000 habitantes. Si el resultado es positivo o dudoso, realizar radiografía de tórax.
- 7. Infección tuberculosa latente (ITL): De acuerdo con el protocolo de actuación que se va a implementar en el Distrito Sanitario de Atención Primaria Poniente, se recomienda lo siguiente, a inmigrantes <35 años, procedentes de países con una incidencia >50 casos/100.000 habitantes, que se puedan tratar y que no tengan contraindicaciones para el tratamiento de la infección tuberculosa latente:
- i) Tratar si procede a las personas con resultados de Mantoux >20mm.
- ii) Realizar IGRA y tratar si procede a personas vacunadas con resultados de Mantoux de 5-19mm para inmigrantes del Magreb y África subsahariana y de 10-19mm para el resto de los inmigrantes incluidos en la población diana.
- *Además, se incluirán en la recomendación la población inmigrante procedente de Marruecos, aunque la incidencia en este país es <50 casos/100.000 habitantes y se considerará realizar IGRA y tratar si procede a personas vacunadas con resultados de Mantoux de 5-19mm.
- **8. Estrongiloidiasis:** Se recomienda el cribado serológico de estrongiloidiasis a la población inmigrante procedente de países endémicos.

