intervention level. Linear regressions will be performed for the monthly detection rates of the aggregated infections, and of each individual condition, comparing the intervention and control centres before and during the intervention period.

- Other secondary outcomes will be the proportion of screening tests performed for the aggregated infections and for each individual condition, and factors associated with having a higher screening performance. For this, associations with continuous variables will be evaluated using t-tests, or one-way analysis of variance (one-way ANOVA) for normally distributed quantitative variables, while for not normally distributed quantitative variables, Wilcoxon Rank-Sum and Kruskal-Wallis tests will be carried out. Pearson's chi-square test or Fisher's exact test will be performed to evaluate the associations between categorical variables. In addition, odds ratio (OR) will be estimated (Table 3). Mixed effects logistic regression models will be carried out to identify associations between the screening performance and socio-demographic and epidemiological characteristics, and adjusted odds ratio (aOR) will be estimated, using the region of the PCC as a random intercept (Table 3).
- **b.** The **prevalence** of each individual condition will be estimated and reported with its respective 95%CI. The prevalence for each infection was defined as the number of diagnoses identified by the screening tests performed among the people that were tested. Serology tests will be contemplated for HIV, HBV, HCV, *T.cruzi*, *S.stercoralis* and *Schistosoma spp.* infections; for active TB, chest radiographies will be examined; for FGM, the completed questionnaires and/or referrals to specialists will be considered.

See table 4 for details of the methodology employed for the outcomes.

Data analysis in Andalusia

A similar analysis approach will be carried out in Andalusia but the limited number of PCCs may prevent to estimate the health impact of the tool, therefore, we plan to estimate preliminary effectiveness data. In addition, the analysis for syphilis, latent TB and intestinal parasites will be executed. Nevertheless, because the pilot study will be conducted in six PCCs of one area (Almería), we won't be able to carry mixed-effects logistic regression models and instead, multiple logistic regressions will be performed.

7. Tables and Figures

Table 1. Description of the ISMiHealth sample.

| Variables | Summary statistics | | |

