| Migrants tested for active TB | N (%) |
| Migrants tested for latent TB [^] | N (%) |
| Migrants tested for a T.cruzi infection | N (%) |
| Migrants tested for a S. stercoralis infection | N (%) |
| Migrants tested for a Schistosoma spp. infection | N (%) |
| Migrants tested for intestinal parasites^ | N (%) |
| Migrants screened for FGM | N (%) |
| Migrants diagnosed with HIV | N (%) |
| CD4 cell count | Mean (SD) or Median (IQR) |
| HIV viral load | Mean (SD) or Median (IQR) |
| Migrants diagnosed with syphilis^ | N (%) |

| Migrants diagnosed with HBV | N (%) |
|--|---------------------------|
| Migrants diagnosed with HCV | N (%) |
| Migrants diagnosed with active TB | N (%) |
| Migrants diagnosed with latent TB [^] | N (%) |
| Migrants diagnosed with T.cruzi infection | N (%) |
| Migrants diagnosed with S.stercoralis infection | N (%) |
| Migrants diagnosed with Schistosoma spp. infection | N (%) |
| Migrants diagnosed with intestinal parasites^ | N (%) |
| Laboratory parameters | Mean (SD) or Median (IQR) |
| Migrants diagnosed with FGM | N (%) |
| Referrals to specialists | N (%) |
| Other diagnoses | N (%) |
| Comorbidities | N (%) |
| Drugs prescribed during the intervention | N (%) |
| Medication adherence (in days) | Mean (SD) or Median (IQR) |
| Hospitalised patients | N (%) |
| Diagnoses during hospitalisation | N (%) |
| Time hospitalised | Mean (SD) or Median (IQR) |
| Patients who needed Intensive Care Unit | N (%) |
| Drugs prescribed during hospitalisation | N (%) |
| Medication adherence of drugs prescribed during | Mean (SD) or Median (IQR) |
| hospitalisation (in days) | |
| Follow-up visits after hospitalisation | Mean (SD) or Median (IQR) |
| Diagnoses made during follow-up visits after hospitalisation | N (%) |
| Drugs prescribed during follow-up visits after hospitalisation | N (%) |
| Medication adherence of drugs prescribed in follow-up | Mean (SD) or Median (IQR) |
| visits after hospitalisation (in days) | |
| Cured patients | N (%) |
| Patients who died during the intervention period | N (%) |

HIV: human immunodeficiency virus, HBV: hepatitis B virus, HCV: hepatitis C virus, TB: tuberculosis, FGM: female genital mutilation, SD: standard deviation, IQR: interquartile range; N = frequency

Table 3. Associations of different factors with XX tests performed

| Variables | XX test performed n/N (%) | OR (95% CI) | p. value | aOR (95% CI) | p. value |

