|---------------------------------|---------------------------------|----------------|----------|-----------------|----------|
| Centre | | | | | |
| Type of centre (urban or rural) | | | | | |
| Index of socioeconomic | | | | | |
| deprivation (MEDEA index) | | | | | |
| Arm of the intervention | | | | | |
| Patient | | | | | |
| Sex | | | | | |
| Age | | | | | |
| Area of birth^ | | | | | |
| Assigned PCT | | | | | |

| Referrals to specialists | | | |
|-----------------------------------|--|---|--|
| Drugs prescribed during the | | | |
| intervention | | | |
| Other diagnoses | | | |
| Immunosuppression status | | | |
| Migrants with screening criteria | | | |
| for XX^ | | | |
| CD4 cell count, viral load and/or | | | |
| laboratory parameters* | | | |
| Hospitalisation | | | |
| Follow-up visits after | | | |
| hospitalisation | | | |
| Mortality | | _ | |

PCT: primary care team, XX: aggregated infections or any of the conditions, OR: odds ratio, aOR: adjusted odds ratio, CI: confidence interval; Region will be used as a random intercept for the logistic regressions; ^Only one of these variables will be added to the multiple logistic regression model due to highly correlation; *When applicable

Table 4. Description of the methodology employed for each outcome

| Outcome | | Methodology |
|--|---------------------------------|------------------------------------|
| Detection rate of all aggre | gated infections | Difference in differences analysis |
| | HIV cases | |
| | Syphilis cases^ | |
| | HBV cases | |
| Detection rate of each | HCV cases | Difference in differences |
| individual condition | active TB cases | analysis |
| | latent TB cases^ | |
| | T.cruzi infection cases | |
| | S.stercoralis infection cases | |
| | Schistosoma spp. infection | |
| | cases | |
| | Intestinal parasites cases^ | |
| | FGM cases | |
| Early diagnoses of | HIV | Bivariate analysis and, if |
| infections | HBV | possible, difference in |
| | HCV | differences analysis |
| Screening tests performed of all aggregated infections | | Bivariate analysis |
| | HIV | |
| | Syphilis^ | |
| | HBV | |
| Screening tests | HCV | |
| performed for each | active TB (chest radiographies) | Bivariate analysis |
| individual condition | latent TB^ (TST/IGRA) | |
| | T.cruzi infections | |
| | S.stercoralis infections | |
| | Schistosoma spp. infections | |

| | Intestinal parasites^ | |
|----------------------------|-----------------------------|--------------------------------|

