| alert_fgm | Patients fulfilling the criteria for the screening of FGM | Qualitative | Yes/No |
| sero_hiv | Serologies for HIV | Qualitative | Yes/No |
| sero_syph^ | Serologies for syphilis | Qualitative | Yes/No |
| sero_hbv | Serologies for HBV | Qualitative | Yes/No |
| sero_hcv | Serologies for HCV | Qualitative | Yes/No |
| cxray | Chest radiographies for active TB | Qualitative | Yes/No |
| tst^ | TST for latent TB | Qualitative | Yes/No |
| igra^ | IGRA for latent TB | Qualitative | Yes/No |
| sero_chagas | Serologies for T.cruzi infection | Qualitative | Yes/No |
| sero_strongy | Serologies for S.stercoralis infection | Qualitative | Yes/No |
| sero_schisto | Serologies for Schistosoma spp. infection | Qualitative | Yes/No |
| stool_intpar^ | Stool samples for intestinal parasites | Qualitative | Yes/No |
| fgm | Questionnaires completed for FGM | Qualitative | Yes/No |
| dx_hiv | Diagnosis of HIV | Qualitative | Yes/No |
| cd4 | CD4 cell count | Quantitative | |
| hiv_vl | HIV viral load | Quantitative | |
| dx_syph^ | Diagnosis of syphilis | Qualitative | Yes/No |
| dx_std | Diagnosis of other sexually transmitted diseases (STDs) | Qualitative | Yes/No |
| dx_hbv | Diagnosis of HBV | Qualitative | Yes/No |
| dx_hcv | Diagnosis of HCV | Qualitative | Yes/No |
| dx_activetb | Diagnosis of active TB | Qualitative | Yes/No |
| dx_latenttb^ | Diagnosis of latent TB | Qualitative | Yes/No |
| dx_chagas | Diagnosis of T.cruzi infection | Qualitative | Yes/No |
| dx_strongy | Diagnosis of S.stercoralis infection | Qualitative | Yes/No |

| dx_schisto | Diagnosis of Schistosoma spp. infection | Qualitative | Yes/No |
|-----------------|--|--------------|---|
| dx_intpar^ | Diagnosis of intestinal parasites | Qualitative | Yes/No |
| dx_fgm | Diagnosis of FGM cases | Qualitative | Yes/No |
| referral | Referral to specialists due to a diagnosis during the intervention | Qualitative | Yes/No |
| other_dx | Other diagnoses made during the intervention (besides from the infections included in the study and FGM) | Qualitative | ICD-9 or ICD-10 |
| com_dx | Comorbidities | Qualitative | ICD-9 or ICD-10 |
| immune_dx | Immunosuppressive diagnoses during the intervention period | Qualitative | ICD-9 or ICD-10 |
| drugs | Drugs prescribed to patients during the intervention | Qualitative | Anatomical Therapeutic Chemical (ACT) codes |

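### In the Andalusian pilot, active TB is screened by Mantoux first, but the SAP counts only chest radiographs as active-TB tests, so a completed Mantoux-negative screen counts as not tested for active TB

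*Protocol*

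**What the plan says.** **Screening pathway.** Protocol Annex 2 item 6 is the active-TB recommendation for Andalusia. It covers asymptomatic migrants who arrived less than five years ago from countries with an incidence above 50 per 100,000. The first step is the Mantoux: "Se recomienda el cribado de TB por Mantoux a inmigrantes asintomáticos recién llegados". The second step is conditional: "Si el resultado es positivo o dudoso, realizar radiografía de tórax", that is, a radiograph only if the result is positive or doubtful. Annex 1 item 6 of the protocol, for Catalonia, goes straight to the radiograph.

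**What the SAP counts.**
- SAP section 7, Table 4, tests performed for each condition (Endpoint 6): "active TB (chest radiographies" in one row and "latent TB^ (TST/IGRA" in another. The caret marks the latent-TB row as Andalusia only. The active-TB row has no site mark.
- SAP Annex 1: cxray is defined as "Chest radiographies for active TB" and tst as "TST for latent TB". No other test variable is assigned to active TB.
- SAP Table 2 has a row "Migrants tested for active TB" and names no test.
- SAP section 6, prevalence, in the Catalan part: "for active TB, chest radiographies will be examined". Endpoint 11 divides by the number tested for the condition.
- The Andalusian part of section 6 says the approach will be similar. It adds syphilis, latent TB and intestinal parasites and changes the regression model. It gives no rule for active TB.

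**The concern.** Under Annex 2 a negative Mantoux completes the recommended active-TB screen in an asymptomatic person. The SAP gives that person tst = Yes and cxray = No, which counts as tested for latent TB and not tested for active TB. A clinician who followed the recommendation exactly is scored as not having screened.

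Three kinds of output are exposed, all in the Andalusian active-TB rows:
- the number tested (Table 2, Endpoint 6);
- the factors associated with being screened (Endpoint 8);
- prevalence among those tested (Endpoint 11, exploratory).

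Endpoint 8 is the most awkward. Whether someone counts as screened depends on the result of the screening test, so anything that predicts a positive Mantoux can look like a predictor of being offered screening. Area of birth and age are both in SAP Table 3.

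**Working it through.** The plan states no figure to reproduce. The documents give neither Mantoux positivity nor the frequency of radiographs taken for other reasons, so every input below is an assumption.

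**Step 1. How each person is classified.**

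| Asymptomatic person screened under Annex 2 item 6 | Screen complete? | tst | cxray | Active TB, SAP |
|---|---|---|---|---|
| Mantoux negative | Yes | Yes | No | Not tested |
| Mantoux positive or doubtful, radiograph done | Yes | Yes | Yes | Tested |
| Mantoux positive or doubtful, no radiograph | No | Yes | No | Not tested |

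The first row is the error.

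**Step 2. Counts and prevalence.** Let f be the share of Mantoux tests that lead to a radiograph, and h the number of unrelated radiographs counted per Mantoux test. Hold the number of cases fixed.

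- Count under the SAP divided by the number screened through the pathway = f + h.
- Prevalence under the SAP divided by prevalence among those screened = 1/(f + h).

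| h | f = 0.2: count ratio, prevalence ratio | f = 0.5: count ratio, prevalence ratio |
|---|---|---|
| 0 | 0.20, 1/0.20 = 5.0 | 0.50, 1/0.50 = 2.0 |
| 0.25 | 0.45, 1/0.45 = 2.2 | 0.75, 1/0.75 = 1.3 |
| 1.0 | 1.20, 1/1.20 = 0.83 | 1.50, 1/1.50 = 0.67 |

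The two errors cancel at h = 1 − f, which is 0.8 for f = 0.2 and 0.5 for f = 0.5. Above that the direction reverses. If unrelated radiographs also find cases, the numerator rises and the cancelling point moves.

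**Step 3. False association in Endpoint 8.** Take two areas of birth of equal size with the same Mantoux uptake u, and 20% versus 50% positive or doubtful, all of whom get a radiograph. The true odds ratio for being screened is 1.0. The SAP outcome has probabilities 0.2u and 0.5u. The crude odds ratios are:

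- u = 0.4: 0.08 and 0.20, so (0.20/0.80)/(0.08/0.92) = 2.87.
- u = 0.1: 0.02 and 0.05, so (0.05/0.95)/(0.02/0.98) = 2.58.
- u = 0.8: 0.16 and 0.40, so (0.40/0.60)/(0.16/0.84) = 3.50.

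Now let 30.2% of people in both areas have an unrelated radiograph, independently of the Mantoux, with u = 0.4. The SAP outcome becomes 1 − 0.92 × 0.698 = 0.358 and 1 − 0.80 × 0.698 = 0.442. Their mean is 0.40, equal to the true uptake, so the total is right. The odds ratio is (0.442/0.558)/(0.358/0.642) = 1.42. A correct total therefore does not remove the false association, because the wrong individuals are counted.

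**The case against.** **The radiograph rule is explicit in only two places.** Table 4 for Endpoint 6 and the cxray definition state it without a site limit. Table 2, Endpoint 8 and Endpoint 11 name no test, and the prevalence sentence stands under Catalonia. The SAP also says that the two sites' algorithms rest on different recommendations and are analysed independently. This stands as a limit on how firmly the rule is stated. It does not rescue the plan: cxray is the only active-TB test variable, and Andalusia is to be analysed along similar lines, so the same rule reaches those outputs unless someone departs from the SAP.

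**One test per condition is tidy, and protocol section 6 itself names radiography for active TB.** That is a fair way to report each test once. But active TB has its own rows, and the latent-TB row covers a different group, so it cannot stand in. Protocol section 4.1.1 e sends the reader to the annexes for recommendations by setting. A reader might infer that section 6 and Annex 2 conflict in substance. They do not, and a cross-reference is enough.

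**Counting every Mantoux would overshoot.** This stands. Annex 2 item 7 uses the same test for latent TB in people under 35, with no arrival limit and with Moroccans added. Counting those tests as active-TB screening could create a new age or origin artefact in Endpoint 8. The fix has to guard against it.

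**The magnitude is assumed.** This stands too. The prevalence ratio runs from 5.0 down to 0.67 across plausible-looking inputs, and the odds ratio of 2.9 depends on the chosen 20% versus 50% contrast.

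**Conclusion.** Wrong as written, with low stakes. Endpoint 6 scores a completed Mantoux-negative screen as not tested for active TB. Through the cxray variable the same happens in Table 2, Endpoint 8 and the Endpoint 11 denominator. That conclusion rests on the text alone. The size does not: it depends on Mantoux positivity and on unrelated radiographs.

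Three stronger readings are tempting and are not supported:
- **Mantoux-screened people vanish from the analysis.** They do not. TST and IGRA count in the latent-TB rows, in Endpoint 5, and, when positive, in Endpoints 1 and 2.
- **Active-TB prevalence will be overstated two- to five-fold.** That holds only if 20–50% of Mantoux tests lead to a radiograph and no unrelated radiographs are counted. The net direction for counts and prevalence is not established.
- **The effectiveness result is biased.** The primary endpoint, the detection rates and the Catalan analysis do not use this definition.

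What remains is one condition's secondary and exploratory rows in a six-centre pilot, analysed separately, from which SAP section 5.1 expects only preliminary effectiveness data.

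**What to change.** For Andalusia, add to the SAP:

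1. **Active-TB screening performed (Table 2, Endpoints 6 and 8):** a Mantoux or a chest radiograph. The main version is among people who meet the active-TB criteria (alert_activetb = Yes), so that Mantoux tests done only for latent TB under item 7 do not count. Give an unfiltered version as a sensitivity analysis, because the protocol's study limitations say that arrival date is not routinely collected. In the filtered version of Endpoint 8, fulfilling the criteria is constant and cannot be a covariate, so area of birth is the one to use.
2. **Endpoint 11 denominator:** people with a Mantoux read as negative or with a chest radiograph. Count cases (dx_activetb) only within that group. Report separately those with a positive, doubtful or unread Mantoux and no radiograph.
3. **Endpoint 5:** count each Mantoux once, even if it appears in both the active-TB and latent-TB rows.
4. **Protocol section 6:** add a reference to Annex 2 for Andalusia.

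The cost is a little extra derivation and one cross-reference, with no new procedures for patients. One condition must be checked. SAP Annex 1 lists tst only as Yes/No, and item 2 needs the reading. Endpoints 1 and 2 already need positive TST results, but the sponsor should confirm that results, and not only an indicator that the test was done, are in the extract.

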1. JUSTIFICATION

Over 200 million girls and women worldwide are estimated to be living with the effects of female genital mutilation (FGM), which can cause several physical, mental and sexual health complications (1). Women who have undergone FGM often delay or do not seek help when they experience health problems that may be linked to the procedure because of several reasons, such as shame, lack of access or affordability, normalization of certain health-related symptoms, lack of confidence in healthcare providers (2). On the other hand, women who do seek care for particular medical problems may not be aware about the complications of FGM and therefore, they may not disclose their experience of FGM to the care provider (2).

Primary health care providers play an important role in supporting girls and women living with FGM, and improving their health and well-being (1). Providing care and treatment requires not only understanding women's needs at all levels but also providing adequate information so that they can make informed decisions (2). It is essential that healthcare providers communicate and discuss women's health and FGM status with them in a sensitive and non-judgmental manner, although this discussion can be challenging for both parts (2).

Within the framework of the ISMiHealth project, which contributes to the screening and detection of migrant women who have suffered FGM, the research team identified the need to further investigate the health needs of these women and their perceptions about the way FGM is currently approached in Spain. Relevant recommendations on how to address this topic and a training course for healthcare providers will be carried out by a group of experts.

This study intends to contribute towards the development of culturally sensitive screening methods of FGM that can be integrated into the ISMiHealth digital tool, so that healthcare providers can identify

those women who may have been victims of FGM and address their health needs. By improving the types of questions in the existing tool and the way they are structured and worded, this will allow practitioners to start talking about FGMs in a respectful and trustful manner with their patients.

BIBLIOGRAPHY

- 1. Person-centred communication for female genital mutilation prevention: a facilitator's guide for training health-care providers. Geneva: World Health Organization; 2022.

2. OBJECTIVES

The main objective of this study is to understand the barriers and enablers that migrant women, who are at risk or have survived FGM, encounter when disclosing their related health needs at primary care.

Specific objectives:

- **I.** To explore the belief systems around FGM among women who come from areas where the practice is prevalent. This includes insights on the cultural relevance and social norms associated with FGM.
- **II.** To examine the extent to which the health needs of this population group of women are met at primary health care, and the barriers encountered when seeking health care.
- **III.** To explore healthcare professionals' perceptions on the detection barriers and enablers of FGM at primary health care.

